3 INVESTIGATIONAL PLAN

3.1. General Design

This is a single-center, phase II, open label study evaluating the efficacy and safety of the combination of INCMGA00012, INCAGN01876 and SRS for patients with recurrent GBM.

The overall study population will be broken down into two cohorts: Cohort A (N=16) and Cohort B (N=16). Subjects for whom surgical resection is not clinically indicated at the time of study

screening will be enrolled into Cohort A (non-surgical cohort). Subjects for whom surgical resection is clinically indicated at the time of study screening will be enrolled into Cohort B (surgical cohort).

The first 6 subjects enrolled onto the study must be enrolled onto Cohort A and will be enrolled in two groups of 3 subjects (i.e., a “3+3” design) as part of a safety run-in period. After enrollment of the first 3 subjects, enrollment is put on hold until all of the first 3 subjects have completed the safety monitoring period (completion of SRS and one cycle of INCMGA00012 and INCAGN01876). If only 0-1 of the first 3 subjects experiences a criterion for study drug discontinuation, as defined in [Section 5.7, Study Drug Discontinuation Criteria](#), then the next 3 subjects will be enrolled. If 2 of the first 3 subjects experience a criterion for study drug discontinuation, the study will be paused for reconsideration of the dosing and schedule of investigational agents.

Of the first 6 subjects enrolled during the safety run-in, if 3 or greater subjects experience a criterion for study drug discontinuation, then the study will be paused for reconsideration of the dosing and schedule of investigational agents. If only 0-2 of the first 6 subjects enrolled during the safety run-in experience a criterion for study drug discontinuation, then enrollment to both cohorts A and B will commence uninterrupted.

If at any point during the safety run-in a stopping rule is met and the dose/schedule of investigational agents is changed, the safety run-in will start over again with another 6 patients. If Cohort A has reached enrollment of 12 subjects and the criteria to move beyond the safety run-in phase has still not yet been met (i.e., at least 6 patients have been treated at the same dose/schedule and only 2 or fewer have experienced a criterion for study drug discontinuation), the trial (including Cohort B) will be terminated due to intolerability of the study regimen.

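### The run-in restart rule, go criterion and 12-subject trigger do not fit together once failed run-ins have used 9 subjects: up to 3 more may be enrolled with no route to a go decision

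*Combined protocol and SAP*

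**What the plan says.** Section 3.1 (General Design) builds the safety run-in in steps. The first Cohort A subjects "will be enrolled in two groups of 3 subjects", with a hold after the first 3. There are two stopping points. The first is worded "If 2 of the first 3 subjects experience a criterion for study drug discontinuation". The second applies to the first 6 subjects: "if 3 or greater subjects experience a criterion for study drug discontinuation". Either one pauses the study so that dose and schedule can be reconsidered.

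If the dose or schedule is then changed, "the safety run-in will start over again with another 6 patients". No limit on the number of restarts is given apart from the overall count. That count is set by the sentence that begins "If Cohort A has reached enrollment of 12 subjects and the criteria to move beyond the safety run-in phase has still not yet been met", in which case the whole trial, Cohort B included, is terminated. The same sentence states the go criterion: "at least 6 patients have been treated at the same dose/schedule and only 2 or fewer have experienced a criterion for study drug discontinuation".

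Section 3.5 confirms 12 as the largest number the run-in may use. The worked example in 3.1 and the maximum of 22 in 3.5 both describe one path only: 6 subjects, then 6 at the final dose/schedule, then 10 more. Neither section says what happens when fewer than 6 run-in places are left.

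**The concern.** Each sentence is workable alone. Together they leave a gap. A restart calls for 6 subjects and the go criterion needs 6 at one dose/schedule, but termination depends on total Cohort A enrolment and not on whether 6 can still be reached. Because a run-in can end after 3 subjects as well as after 6, the total used need not be a multiple of 6.

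If the total stands at 9 and the dose/schedule is changed again, subjects 10 to 12 could receive both agents and SRS in a run-in whose outcome is already fixed. They would add some safety data but could not alter the run-in decision. The gap is likeliest to be reached when the event rate is high, which is the situation the run-in is there to detect.

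**Working it through.** **Inputs.** From 3.1: looks after 3 and after 6 subjects; stop at 2 of 3 or at 3 or more of 6; go at 6 or more treated at one dose/schedule with 2 or fewer events; restart with 6; termination at 12. From 3.5: a run-in maximum of 12. The text names 2 of 3 but not 3 of 3 at the first look; I take 3 of 3 to stop as well. The documents give no rate for the discontinuation criteria, so the per-subject event rate p is an assumption, shown over a range.

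**The plan's own figure.** The Cohort A maximum in 3.5 is 6 + 6 + 10 = 22, equivalently 12 − 6 + 16 = 22. It reproduces.

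**Places left after failed run-ins**

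| Failed run-ins | Used | Left under 12 | Can 6 be treated at a newly changed dose/schedule? |
|---|---|---|---|
| 3+3 | 6 | 6 | Yes |
| 3+6 or 6+3 | 9 | 3 | No |
| 3+3+3 | 9 | 3 | No |
| 6+6 | 12 | 0 | Terminates |

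At 9 used, a full restart would reach 9 + 6 = 15, which exceeds 12. At most 3 subjects can be treated at the new dose/schedule, fewer than the 6 required, so termination at 12 follows whatever their outcomes.

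**How often.** For one run-in, with X the events in the first 3 and Y the events in the second 3:

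- F3 = P(X ≥ 2) = 3p²(1−p) + p³
- F6 = P(X=0)·P(Y=3) + P(X=1)·P(Y≥2)
- two failures using exactly 9 subjects: 2·F3·F6
- three failures at 3 subjects each: F3³

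At p = 1/3, F3 = 6/27 + 1/27 = 7/27 = 0.2593. F6 = (8/27)(1/27) + (12/27)(7/27) = 92/729 = 0.1262. So 2 × 0.2593 × 0.1262 = 0.065. Adding F3³ = 0.017 gives 0.083.

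| p (same at every dose) | F3 | F6 | 3+6 or 6+3 | with 3+3+3 added |
|---|---|---|---|---|
| 10% | 0.0280 | 0.0075 | 0.04% | 0.04% |
| 20% | 0.1040 | 0.0440 | 0.9% | 1.0% |
| 1/3 | 0.2593 | 0.1262 | 6.5% | 8.3% |
| 40% | 0.3520 | 0.1659 | 11.7% | 16.0% |
| 50% | 0.5000 | 0.2031 | 20.3% | 32.8% |

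**If the change lowers toxicity.** With p = 1/3 in the first run-in and 20% in the second, the two-failure probability is 0.2593 × 0.0440 + 0.1262 × 0.1040 = 0.0114 + 0.0131 = 0.025, against 0.065 at a constant one third.

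**The case against.** Four arguments can be made on the other side.

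*The three enrolments are not compelled.* A reader might infer that the trial must restart, treat subjects 10 to 12 and only then stop. The documents do not support that. Each failure triggers a pause, and the restart is conditional on a change. Sections 5.5.1, 5.5.2 and 5.8.1 allow no dose escalation or reduction, and 1.1 requires an approved amendment for protocol changes, apart from immediate hazards. A changed dose would therefore ordinarily pass through a review at which the remaining places could be noticed. Section 3.4 lets the sponsor terminate on emerging data. One can also read the cap in 3.5 as making a restart that does not fit unavailable. All this stands: the text permits the exposures and does not force them. But none of these steps is tied to the number of places left, and the only explicit run-in trigger is enrolment of 12.

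*The later subjects would not be on a regimen that had failed twice.* A reader might infer that they would. Section 3.1 ties the restart to a changed dose/schedule, so they would be on a further modification after earlier ones had met their stop. This stands.

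*A go is not excluded in every case.* If a run-in stopped at 3 with exactly 2 events, and that dose/schedule were continued or resumed, 3 event-free subjects would literally give 6 treated with 2 events. The text does not say whether this is allowed. The dead end therefore assumes a changed dose/schedule judged on its own subjects only.

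*The scenario may be rare.* It is at low event rates. The nearest figure in the documents is 4 participants with DLTs among 56 given INCAGN01876 300 mg plus nivolumab (Section 1.3.2.2), or 7%. That rate would give about 0.01%. It is only indicative, since DLTs are not the Section 5.7 criteria and there was no SRS.

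**Conclusion.** The gap is real on the text, and its scope is limited. Once failed run-ins have used 9 Cohort A subjects, a restart at a changed dose/schedule cannot meet the go criterion before the 12-subject trigger. The rules as written then permit up to 3 exposures that cannot produce a go decision.

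This rests on the dose/schedule being changed, on only that run-in's own subjects counting, on 3 of 3 being treated as a stop, and on run-ins ending after complete groups of 3. Other conventions move the count. If a stop were called at a third event in subject 5, 3 + 5 = 8 would leave 4 places. Section 3.2 excludes replaced subjects from the safety criteria, but the text does not say whether they count towards the 12.

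The probability depends on an event rate that the documents do not supply: below 1% for the two-failure paths at 20%, rising to about one in five at 50%, on the assumption of a constant rate. It is lower if the modification reduces toxicity. The documents do not support reading this as a certainty that three subjects will be exposed, or as a flaw in the 6+6 path that the plan illustrates. It is worth correcting because it sits in a safety rule, matters most when toxicity is high, and costs almost nothing to remove.

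**What to change.** Reconcile the restart, go-criterion and termination sentences in 3.1, the worked example there, and the run-in maximum in 3.5. The run-in should not be able to go on enrolling when the places left under the cap cannot satisfy the go criterion. State as well whether subjects may be added at an unchanged dose/schedule after a pause and, if so, which subjects count. It would help to say in the same place whether replaced subjects count towards the 12. Which stopping or dosing rule to adopt is for the sponsor to decide; the request is only that the passages agree.

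The cost is about one sentence in the protocol, with no added patients, visits or procedures. On the changed-dose paths that reach 9 subjects, closing the gap avoids up to 3 exposures and gives up no possible go decision. The 3+3 path keeps its full run-in of 6, and the 6+6 path still ends at 12.

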3.2 Replacement of Subjects

Cohort A: Any subject who is enrolled onto Cohort A of the study but meets one of the following criteria is replaced by enrollment of a new subject onto Cohort A:

- The subject is enrolled, but does not receive BOTH systemic agents (INCMGA00012, INCAGN01876)
- The subject is enrolled, but does not receive SRS
- The subject is enrolled as part of the safety run-in cohort and, for any logistical reason unrelated to the patient's clinical condition, does not receive all scheduled components of Cycle 1 treatment (i.e., a subject is enrolled on safety run-in cohort but does not receive all of the following: 3 fractions of radiation, C1D1 dose of INCMGA00012, C1D1 dose of INCAGN01876, and C1D15 dose of INCAGN01876). Examples of such logistical reasons include: the current lot of investigational product on site (INCMGA00012 or INCAGN01876) tests out of specification, the radiation machine breaks down in the midst of the subject's radiation, a spike in COVID-19 infections results in temporary suspension of clinical research at the study site, etc).

- The subject receives study drugs (+/- SRS), but becomes pregnant (and therefore is taken off study per study drug discontinuation criteria [Section 5.7](#)) before the first response evaluation (MRI) occurs
- The subject receives study drugs (+/- SRS), but consent is withdrawn by the subject before the first response evaluation (MRI) occurs
- The subject receives study drugs (+/- SRS), but is subsequently found not to have met eligibility criteria, AND the Medical Director, in collaboration with the investigator, determined that the subject should be withdrawn from the study, AND the first response evaluation (MRI) has not yet taken place
- The subject receives study drugs (+/- SRS), but is then noncompliant with study procedures in the investigator's opinion, AND the sponsor has been consulted and has determined that the subject should be withdrawn from the study, AND the first response evaluation (MRI) has not yet taken place

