As long as the subject has not withdrawn his/her consent, the non-treated (replaced) subject is followed for safety follow-up per [Table 10](#) (see [Section 6](#)) and all safety-related data collected for the subject is included in analysis of the study's secondary safety/tolerability endpoints. However, the subject is not included in the primary endpoint efficacy analysis or in analysis of secondary efficacy endpoints (see [Section 8, Statistical Plan](#)). In addition, if the replaced subject was enrolled during the safety run-in phase, that subject will not be counted for purposes of determining whether the pre-specified safety criteria (see [Section 3.1; General Design](#)) have been met during the safety run-in phase to allow for successful completion of the safety run-in phase.

Subject replacement occurs up to and no more than 7 times for Cohort A [i.e., up to 23 subjects can be enrolled to obtain 16 subjects who receive both of the study drugs at the same dose and schedule AND SRS and are therefore evaluable for the primary endpoint].

Cohort B: Any subject who is enrolled onto Cohort B of the study but meets one of the following criteria is replaced by enrollment of a new subject onto Cohort B:

- The subject is enrolled, but does not receive either of the systemic agents (INCMGA00012, INCAGN01876)
- The subject is enrolled, but does not receive SRS (surgical subarm #1 only)
- The subject is enrolled, but does not undergo surgery

As long as the subject has not withdrawn his/her consent, the non-treated (replaced) subject is followed for safety follow-up per [Table 10](#) (see [Section 6](#)) and all safety-related data collected for the subject is included in analysis of secondary study endpoints.

Subject replacement occurs up to and no more than 10 times for Cohort B [i.e., up to 26 subjects can be enrolled to obtain 16 subjects who receive neoadjuvant therapy AND undergo surgery, with 8 patients assigned to each of the 2 sub-arms]. Subjects who need to be replaced in Cohort B, will be replaced by a subject enrolled onto the same sub-arm that the replaced subject was previously on.

Replaced subjects will be followed for safety only. These subjects will not be included in efficacy endpoint analyses, and they will not have tumor tissue available for correlative endpoint analyses.

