3.5 Total Number of Subjects and Sites

This is a single center study and subjects are only recruited from the University of Pennsylvania. Recruitment for Cohort A ends when (1) the safety run-in phase has been successfully completed AND (2) 16 subjects in Cohort A have received at least one dose of each study drug at the same dose/schedule as determined by the safety run-in phase. Greater than 16 total subjects may be enrolled on Cohort A if the stopping rule for toxicity is met during the safety run-in phase (see [Section 3.1 General Design](#)). The maximum possible sample size for Cohort A is 22 subjects who are evaluable for the study's primary efficacy endpoint, which would occur if enrollment of 12 subjects (which is the maximum allowed for the safety run-in phase) is necessary to successfully complete the safety run-in phase and an additional 10 subjects are enrolled at the same finalized dose/schedule of study drugs that was given to the last 6 subjects enrolled on the safety run-on phase.

Recruitment for Cohort B ends with 16 subjects have received study drug(s) AND surgery.

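### The run-in cap of 12 counts enrolled subjects, so after a first run-in that used six, one replaced subject triggers termination of the trial as intolerable

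*Combined protocol and SAP*

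**What the plan says.** Section 3.1 (General Design) runs the safety run-in in Cohort A as two groups of three. Two events among the first three, or three or more among the first six, pause the study. If the dose or schedule is then changed, "the safety run-in will start over again with another 6 patients". To leave the run-in, the plan needs that "at least 6 patients have been treated at the same dose/schedule and only 2 or fewer have experienced a criterion for study drug discontinuation". The backstop is worded on enrolment: "If Cohort A has reached enrollment of 12 subjects and the criteria to move beyond the safety run-in phase" are still unmet, then "the trial (including Cohort B) will be terminated due to intolerability of the study regimen".

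Section 3.2 (Replacement of Subjects) lists seven reasons for replacing a Cohort A subject. One is specific to the run-in and covers missed Cycle 1 components for logistical reasons; an example is that "the radiation machine breaks down in the midst of" a subject's treatment. Each replaced subject is described as having been enrolled or as having received study drug. For anyone replaced during the run-in, "that subject will not be counted for purposes of determining whether the pre-specified safety criteria" have been met. The section allows up to 7 replacements in Cohort A and translates this into at most 23 enrolled.

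Section 3.5 repeats the figure of 12, "which is the maximum allowed for the safety run-in phase", and adds 10 further subjects to reach a Cohort A maximum of 22, whom it calls evaluable for the primary endpoint.

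**The concern.** The cap and the exit criterion count different things. The cap counts people enrolled; the criterion counts people who were not replaced. A replaced subject uses one of the 12 places and cannot help to satisfy the criterion. Because 12 is exactly two run-ins of six, one path through the design has no tolerance for this mismatch.

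The path is not contrived. The worked example in Section 3.1 has six subjects with three events, then six more at a new dose/schedule, and Section 3.5 builds its maximum of 22 on the same sequence. On that path, a consent withdrawal or an interrupted radiation course can lead to closure of both cohorts with intolerability recorded as the reason, whatever was seen at the new dose/schedule. The primary response analysis would be lost and the recorded safety conclusion could be wrong.

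**Working it through.** **The plan's own figures.** 6 + 6 = 12 (Section 3.1, repeated in 3.5). 12 + 10 = 22 (3.5 and the worked example in 3.1). 16 + 7 = 23 (3.2). All three reproduce. None of the first four terms (6, 6, 12, 10) includes an allowance for replacement.

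**Spare places under the cap.** Spare places = 12 − (enrolled in the first run-in) − 6.

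| First run-in | Calculation | Spare | Replacements that trigger the rule |
|---|---|---|---|
| Used 6, then restart | 12 − 6 − 6 | 0 | 1 |
| Stopped after 3, then restart | 12 − 3 − 6 | 3 | 4 |
| No restart | 12 − 0 − 6 | 6 | 7 |

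On the first row, a replacement after the restart leaves 6 − 1 = 5 countable subjects when the twelfth is enrolled. A replacement before the restart means 7 places are used and 12 − 7 = 5 remain. Either way the requirement of six cannot be met within 12 enrolled.

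**How often each restart occurs.** The documents give no event rate, so p is assumed, with subjects independent and three of three treated as meeting the two-of-three rule.

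- Stop after 3 = P(at least 2 of 3).
- Stop after 6 = P(0 of 3) × P(3 of 3) + P(1 of 3) × P(at least 2 of 3).
- At p = 20%, stop after 6 = 0.512 × 0.008 + 0.384 × 0.104 = 0.0440.
- At p = 30%, stop after 6 = 0.343 × 0.027 + 0.441 × 0.216 = 0.1045.

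| Assumed p | Stop after 3 | Stop after 6 | Share of first restarts that follow 3 |
|---|---|---|---|
| 10% | 2.8% | 0.75% | 79% |
| 20% | 10.4% | 4.4% | 70% |
| 30% | 21.6% | 10.5% | 67% |
| 40% | 35.2% | 16.6% | 68% |
| 50% | 50.0% | 20.3% | 71% |

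The path with no spare place is therefore about 21% to 33% of first restarts.

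**Adding replacement.** The replacement rate q per subject is also assumed. P(at least 1 of 12) = 1 − (1 − q)^12, which is 0.460 at q = 5% and 0.718 at q = 10%. The joint probability is the product:

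| Assumed p | q = 5% | q = 10% |
|---|---|---|
| 20% | 0.044 × 0.460 = 2.0% | 0.044 × 0.718 = 3.2% |
| 30% | 0.1045 × 0.460 = 4.8% | 0.1045 × 0.718 = 7.5% |
| 50% | 0.2031 × 0.460 = 9.3% | 0.2031 × 0.718 = 14.6% |

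Some of these second run-ins would fail on toxicity in any case. If the event rate did not change after the restart, a run-in would pass with probability 1 − 0.148 = 0.852 at p = 20% and 1 − 0.3205 = 0.6795 at p = 30%. The wrongly terminated share is then 1.7% and 3.3% at q = 5%, and 2.7% and 5.1% at q = 10%.

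On the path that restarts after three subjects, P(at least 4 of 12 replaced) is 0.2% at q = 5% and 2.6% at q = 10%, so the cap is not a practical problem there.

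**The case against.** The best counter-argument is that the 12 was never meant to include replaced subjects. Section 3.5 describes the 22 built from 12 + 10 as evaluable, and Section 8.1 limits evaluability to subjects who have not been replaced. Section 3.1 also speaks of the first six enrolled, yet Section 3.2 takes replaced subjects out of that count, so the word is already used net of replacement once. Read literally, the cap would even stop the plan's own worked example on the day the twelfth subject enrols, before that subject has completed monitoring, so the sentence needs a sensible reading anyway.

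This shows a plausible intention, and it stands as far as that goes. But no passage exempts replaced subjects from the 12, Section 3.2 removes them only from the assessment of the safety criteria, and the plain wording of the cap is enrolment. Leaving the matter to judgement on the day is weak protection: Section 1.1 bars changes without an approved amendment except for immediate hazards, so the team would be amending a stopping rule after seeing toxicity data.

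Three further limits stand. A reader might infer that any restart leaves no slack; the documents do not support this, because a restart after the first three leaves three spare places and is the commoner kind at every rate tried. A reader might also infer that an equipment fault alone can condemn a well-tolerated regimen; in fact the path arises only after at least three of six subjects met a discontinuation criterion at the first dose/schedule, so absence of toxicity can apply only to the new one. Finally, the allowance of 7 replacements in 23 is a ceiling over all seven reasons and not an expected rate. One might also count only the six subjects after the restart (26% and 47% in place of 46% and 72%), but a replacement before the restart does the same harm, so 12 is the right base.

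**Conclusion.** The point holds for one defined path. When the first run-in has used six subjects, the cap as worded leaves no room for any replacement, and a single one meets the condition for closing both cohorts under a tolerability label, regardless of events at the new dose/schedule. It does not hold for restarts in general. The chance is modest: about 2% to 5% at a 5% replacement rate and 3% to 8% at 10%, for event rates of 20% to 30%, and lower once genuine second failures are removed. All of these rates are assumptions. What justifies action is the consequence, which is loss of the trial with a possibly wrong stated reason, set against a small correction. The conclusion rests on reading enrolment in its ordinary sense; Section 3.5 suggests another intention, and the passages need to be reconciled.

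**What to change.** In Sections 3.1 and 3.5, state that the 12 counts run-in subjects who have not been replaced under Section 3.2. In Section 3.1, reserve the intolerability label for failure of the event criteria, and describe a shortfall from accrual or replacement separately. It would help to say in the same sentence that the rule is assessed once those subjects have completed safety monitoring.

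Section 3.2 also needs attention. Its ceiling of 23 enrolled comes from 16 + 7. The 6 + 6 + 10 path already needs 22, which leaves room for 23 − 22 = 1 replacement, whereas all seven would mean 22 + 7 = 29. The plan should say whether the limit is seven replacements or 23 enrolled when a restart has occurred.

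The cost is a short edit in three sections. Possibly a few more subjects would enter the run-in, up to 12 + 7 = 19 if all seven replacements fell there and the ceiling allowed it, and some of the replaced subjects may have been partly treated. The thresholds of two of three and three of six do not change.

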If at any point during the safety run-in a stopping rule is met and the dose/schedule of investigational agents is changed, and the safety-run in phase is then successfully completed at the new dose/schedule, 16 additional subjects will be enrolled in Cohort A at the new dose/schedule to achieve the desired sample size of 16 subjects that are evaluable for the study’s primary endpoint. Thus, the total sample size for Cohort A could potentially be more than 16 subjects (e.g., 6 subjects are enrolled in the initial safety run-in and 3 of them experience a toxicity requiring study drug discontinuation; an additional 6 subjects are then enrolled at the new dose/schedule that has been decided upon, and this time the safety run-in is completed successfully with only 1 subject discontinuing study drug due to toxicity; we would then enroll 10 additional subjects at the current dose/schedule of study drugs to achieve 16 evaluable subjects treated at the final dose/schedule; the total sample size for cohort A in this example would be 22 subjects).

Cohort B will not start enrollment until the safety run-in phase has been successfully completed.

Details of treatment administered in each cohort are provided below in [Section 3.1.2, Study Intervention Phase](#).

[figure not shown]

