8.2 Statistical Methods

8.2.1 Primary Endpoint Analysis (Efficacy of Regimen)

The primary efficacy hypothesis of this study is that the proportion of subjects who experience an objective radiographic response will be 25% or higher. We will test this hypothesis against the null hypothesis of 5% of subjects experiencing an objective response using an exact single-stage phase II design for the primary study cohort (Cohort A; Non-surgical). A sample size of 16 evaluable subjects is required for 80% power. A one-sided significance level has been set at 0.05. A subject is considered evaluable for the primary endpoint if (a) the subject is one of the 16 subjects enrolled onto Cohort A at the same dose and schedule of study drugs that is determined to be the final dose/schedule based on the safety run-in phase, AND (b) the subject has received at least one dose of BOTH study drugs AND has received at least one fraction of SRS.

In one of the largest series of patients with recurrent high-grade glioma treated with hypofractionated stereotactic radiation therapy alone, ~10% of patients experienced a minimal response of the irradiated tumor by MacDonald Criteria; no patients experienced a partial response ([Fogh, J Clin Oncol 2010](#)). For patients who have one tumor site irradiated while other sites of tumor are not irradiated, such as some of the subjects who will be enrolled in the current protocol, no responses would be expected in non-irradiated tumor. With these data in mind,

coupled with the historic overall response rate of ~10% to single-agent lomustine (a standard of care) in recurrent GBM (Batchelor TT, et al. *J Clin Oncol* 2013), we have designated ORR=5% as the null hypothesis.

The alternative hypothesis, a 25% ORR, would be a clinically significant difference that would suggest this regimen is worthy of further investigation.

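### After a restarted run-in, Sections 3.1 and 3.5 give Cohort A enrolment and evaluable counts that disagree with each other and with the 16-subject primary analysis in Section 8.2.1

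*Combined protocol and SAP*

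**What the plan says.** Four places in the combined protocol and SAP bear on how many Cohort A subjects are enrolled and analysed if the run-in is restarted.

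- **Section 3.1, rule.** Once the repeated run-in has passed at the changed dose/schedule, "16 additional subjects will be enrolled in Cohort A at the new dose/schedule to achieve the desired sample size of 16 subjects" evaluable for the primary endpoint.
- **Section 3.1, worked example, same paragraph.** Six subjects fail the first run-in and six pass the second; then "we would then enroll 10 additional subjects at the current dose/schedule of study drugs". The example gives a Cohort A total of 22.
- **Section 3.5.** Recruitment ends when the run-in has passed and "16 subjects in Cohort A have received at least one dose of each study drug" at a single dose/schedule. The section then says: "The maximum possible sample size for Cohort A is 22 subjects who are evaluable" for the primary endpoint. It builds that 22 from 12 run-in subjects plus 10 more, the 10 sharing the dose/schedule of the last 6 run-in subjects.
- **Sections 8.1 and 8.2.1.** Section 8.2.1 counts a subject as evaluable only if "the subject is one of the 16 subjects enrolled onto Cohort A at the same dose and schedule" settled by the run-in, with at least one dose of both drugs and at least one SRS fraction. Section 8.1 asks only that the subject was not replaced and received SRS and both drugs. It mentions neither 16 nor the final dose/schedule.

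Section 3.2 adds a replacement allowance for Cohort A: "up to 23 subjects can be enrolled to obtain 16 subjects" who receive both drugs at one dose and schedule, and SRS.

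**The concern.** The rule in 3.1 and its own example differ by six subjects. Section 3.5 attaches the word evaluable to a total that includes six subjects on the abandoned dose/schedule. Section 8.2.1 excludes those six; 8.1, read alone, does not.

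At stake is the denominator of the primary response rate in an open-label, single-arm trial. With two evaluability definitions and no written response cutoff, the choice between 16 and 22 could be made after responses are known. Taking the 22 described in 3.5 would also pool two dose/schedules in one estimate. None of this arises unless a run-in stopping rule is met and the dose/schedule is changed.

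**Working it through.** **Inputs.** From Section 8.2.1: the "null hypothesis of 5% of subjects experiencing an objective response" (p0 = 0.05); the hypothesis that the "proportion of subjects who experience an objective radiographic response will be 25% or higher" (p1 = 0.25); an exact single-stage design; one-sided alpha 0.05; 80% power; 16 evaluable. The response cutoff r is not in the documents and is derived here.

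**Formula.** P(X ≥ r) = 1 − Σ C(n,k) p^k (1−p)^(n−k), summed over k = 0 to r−1. Tails below use unrounded terms.

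**1. The plan's own figure, n = 16.**
- Under p0, the terms for k = 0, 1, 2 are 0.4401, 0.3706, 0.1463, so P(X ≥ 3) = 0.0429. A cutoff of 2 would give 0.1892, so 3 is the smallest cutoff that keeps alpha within 0.05.
- Under p1, the terms are 0.0100, 0.0535, 0.1336, so power = 0.8029.
- At n = 15 the cutoff is also 3 and power is 0.764, so 16 is the smallest sample size meeting both targets.

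The stated 16 subjects and 80% power are reproduced, with success at 3 or more responses.

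**2. Counts after a restart, assuming all 6 subjects of the failed run-in were enrolled and nobody is replaced.**

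| Source | Arithmetic | Total enrolled | At final dose/schedule |
|---|---|---|---|
| 3.1 rule, read in sequence | 6 + 6 + 16 | 28 | 6 + 16 = 22 |
| 3.1 example | 6 + 6 + 10 | 22 | 6 + 10 = 16 |
| 3.5 maximum | 12 + 10 | 22, all called evaluable | 6 + 10 = 16 |
| 8.2.1 | – | – | 16 analysed |

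If the first run-in stopped after 3 subjects, the totals are 3 + 6 + 16 = 25 under the rule and 3 + 6 + 10 = 19 under the example. The gap of six remains.

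**3. Does 8.1 exclude the six?** Its first condition removes replaced subjects. The Cohort A replacement criteria in 3.2 do not include having been treated at a dose/schedule that was later changed. A subject from the failed run-in who had both drugs and SRS therefore meets 8.1.

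**4. Operating characteristics by number analysed.**

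| n | Cutoff | Alpha (p = 0.05) | Power (p = 0.25) |
|---|---|---|---|
| 16 | ≥ 3 | 0.0429 | 0.8029 |
| 22 | ≥ 3, carried over | 0.0948 | 0.9394 |
| 22 | ≥ 4, re-derived at 0.05 | 0.0222 | 0.8376 |

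For n = 22 under p0, the terms for k = 0 to 3 are 0.3235, 0.3746, 0.2070, 0.0726. Removing the first three from 1 leaves 0.0948; removing all four leaves 0.0222. The power column for n = 22 takes p = 0.25 for every subject, including any on the abandoned dose/schedule.

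**The case against.** The strongest reply is that the intent is clear and the analysis is protected. Section 8.2.1 governs the primary test and fixes 16 at the final dose/schedule. Section 3.2 and the 3.5 recruitment stop also work to 16 at one dose/schedule. The 3.1 rule names 16 evaluable as its aim, and if its 16 is counted from the start of the new dose/schedule it gives 6 + 16 = 22 enrolled, in line with the example. The example's 10 agrees exactly with the 16-subject analysis.

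Most of this stands as evidence of intent, and it shows which way to reconcile the text. It does not remove the conflict. The 3.1 sentence places the 16 after the repeated run-in has succeeded, 3.5 calls 22 evaluable, and 8.1 would let them in.

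Three stronger readings are tempting, and the documents do not support them.

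- **That type I error is inflated to 0.095.** This needs a restart, an analysis of 22 contrary to 8.2.1, and a cutoff of 3 kept unchanged. No passage directs the last step. An exact test at 0.05 with 22 subjects would use 4, with alpha 0.022.
- **That recruitment could stop short of 16 SRS-treated subjects**, because the 3.5 stop counts only the two drugs. Section 3.2 replaces a Cohort A subject who does not receive SRS, up to seven replacements, so this is largely prevented. What remains is a wording mismatch.
- **That the maxima of 22 (3.5) and 23 (3.2) contradict each other.** They answer different questions: 22 describes a restart, and 23 is 16 + 7 replacements at one dose/schedule.

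**Conclusion.** The sample-size text is wrong as written. After a restart, 3.1 gives both 16 and 10 further subjects, and 3.5 labels 22 evaluable where 8.2.1 allows 16; these cannot all be literally true. Section 8.1 leaves the wider set open.

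The effect on the primary test is conditional. Under 8.2.1 the design is intact, with alpha 0.043 and power 0.803. Only if a restart occurs and 22 are analysed could the error rates move, and the direction cannot be settled from the text because no cutoff is written: alpha would rise to 0.095 or fall to 0.022 depending on the cutoff used.

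The 28 and 22 totals assume a full six-subject failed run-in and no replacements. The cutoffs of 3 and 4 are derived from the stated design parameters.

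**What to change.** - **Section 3.1:** replace the 16 further subjects with enrolment until 16, including the 6 from the successful run-in, are evaluable at the final dose/schedule. The worked example can stay.
- **Section 3.5:** describe the maximum as 22 enrolled before any replacements, of whom 16 are evaluable. Make the recruitment-stop count require both drugs and SRS, as 3.2 already does.
- **Section 8.1:** add the final-dose/schedule condition from 8.2.1, so that the primary analysis set has one definition.
- **Section 8.2.1:** state the success rule of at least 3 responses in 16 evaluable subjects (exact alpha 0.043, power 0.803).

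The cost is a few sentences in an amendment. The planned 16 evaluable subjects, the hypotheses and the treatment are untouched.
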